6.3.6 Part 2 / Month 9 Clinic Visit (Day 270 ± 7 days)

- Assessment of continued consent / assent (where applicable).
- Fasting blood and urine sampling for safety labs, including HbA1c.
- Collect blood sample for plasma retention and storage.
- Collect blood samples for PK and PD.
- Provide subject with a meal/snack.
- Check blood sugar, using point of care device, after an appropriate time.
 - If subject is hypoglycemic (<90mg/dL), feed the subject again and re-check blood sugar prior to neuropsychological assessments.
 - If subject is hyperglycemic (>300mg/dL), reschedule the neuropsychological assessments for a proximal day within the visit window.
- MMSE, ADAS-cog14.
- C-SSRS.
- Review and record new concomitant medications.
- Assess symptoms/adverse events by asking the participants to respond to a non-leading question such as “How have you been feeling?”

- Brief physical and neurologic examination.
- Body weight.
- 12-lead electrocardiogram (ECG) after 5 minutes rest.
- Vital signs: blood pressure (supine), pulse rate after 5 minutes rest.
- Return study drug.
- Drug accountability. Any discrepancies are recorded in the source and the subject and caregiver/informant are counseled regarding proper dosing compliance.
- Dispense study drug. Subjects take their daily dose of study medication in the clinic.
- Provide subject and caregiver with instructions for next visit (e.g., date, requirement for fasting blood samples, hold dosing on morning of visit, return used study drug bottles).

6.3.7 Part 2/ Month 12 Clinic Visit (Day 360 ± 7 days)

- Assessment of continued consent / assent (where applicable).
- Fasting blood and urine sampling for safety labs, including HbA1c.
- Collect blood sample for plasma retention and storage.
- Collect blood samples for PK and PD.
- Provide subject with a meal/snack.
- Check blood sugar, using point of care device, after an appropriate time.
 - If subject is hypoglycemic (<90mg/dL), feed the subject again and re-check blood sugar prior to neuropsychological assessments.
 - If subject is hyperglycemic (>300mg/dL), reschedule the neuropsychological assessments for a proximal day within the visit window.

- MMSE, ADAS-cog14, CDR-sb, FAQ, Amsterdam-IADL, NPI, DEMQOL-proxy.
- C-SSRS.
- Review and record new concomitant medications.
- Assess symptoms/adverse events by asking the participants to respond to a non-leading question such as “How have you been feeling?”
- Brief physical and neurologic examination.
- Body weight.
- 12-lead electrocardiogram (ECG) after 5 minutes rest.
- Vital signs: blood pressure (supine), pulse rate after 5 minutes rest.
- Return study drug.
- Drug accountability. Any discrepancies are recorded in the source and the subject and caregiver/informant are counseled regarding proper dosing compliance.
- Dispense study drug. Subjects take their daily dose of study medication in the clinic.
- Provide subject and caregiver with instructions for next visit (e.g., date, requirement for fasting blood samples, hold dosing on morning of visit, return used study drug bottles).

6.3.8 Part 2 / Month 15 Clinic Visit (Day 450 ± 7 days)

- Assessment of continued consent / assent (where applicable).
- Fasting blood and urine sampling for safety labs, including HbA1c.
- Collect blood sample for plasma retention and storage.
- Collect blood samples for PK and PD.
- Provide subject with a meal/snack.

- Check blood sugar, using point of care device, after an appropriate time.
 - If subject is hypoglycemic (<90mg/dL), feed the subject again and re-check blood sugar prior to neuropsychological assessments.
 - If subject is hyperglycemic (>300mg/dL), reschedule the neuropsychological assessments for a proximal day within the visit window.
- MMSE, ADAS-cog14.
- C-SSRS.
- Review and record new concomitant medications.
- Assess symptoms/adverse events by asking the participants to respond to a non-leading question such as “How have you been feeling?”
- Brief physical and neurologic examination.
- Body weight.
- 12-lead electrocardiogram (ECG) after 5 minutes rest.
- Vital signs: blood pressure (supine), pulse rate after 5 minutes rest.
- Return study drug.
- Drug accountability. Any discrepancies are recorded in the source and the subject and caregiver/informant are counseled regarding proper dosing compliance.
- Dispense study drug. Subjects take their daily dose of study medication in the clinic.
- Provide subject and caregiver with instructions for next visit (e.g., date, requirement for fasting blood samples, hold dosing on morning of visit, return used study drug bottles).

6.3.9 Part 2 / Month 18 Clinic Visit (Day 540 ± 7 days)

- Assessment of continued consent / assent (where applicable).
- Fasting blood and urine sampling for safety labs, including HbA1c.
- Collect blood sample for plasma retention and storage.
- Collect blood samples for PK and PD.
- Provide subject with a meal/snack.
- Check blood sugar, using point of care device, after an appropriate time.
 - If subject is hypoglycemic (<90mg/dL), feed the subject again and re-check blood sugar prior to neuropsychological assessments.
 - If subject is hyperglycemic (>300mg/dL), reschedule the neuropsychological assessments for a proximal day within the visit window.
- MMSE, ADAS-cog14, CDR-sb, FAQ, Amsterdam-IADL, NPI, DEMQOL-proxy.
- C-SSRS.
- Review and record new concomitant medications.
- Assess symptoms/adverse events by asking the participants to respond to a non-leading question such as “How have you been feeling?”
- Brief physical and neurologic examination.
- Body weight.
- 12-lead electrocardiogram (ECG) after 5 minutes rest.
- Vital signs: blood pressure (supine), pulse rate after 5 minutes rest.
- Return study drug.
- Drug accountability. Any discrepancies are recorded in the source.

- Brain MRI. For subjects with a contraindication to MRI scanning (e.g., pacemaker), no brain MRI is required for this visit.

6.3.10 Part 2 / Follow-Up Visit

A Follow-up Visit will be completed 3 months [90 ± 7 days] after a subject completes Month 18 for those participants who complete the study; or at least 45 days after the last dose of study drug if the subject discontinues the study prior to Month 18.

If a subject does not complete a follow up visit, the reason should be documented in the source and EDC. An Early Termination visit does not satisfy the requirement for a Follow-Up Visit.

At any point, if a participant withdraws consent, no further evaluations should be performed, and no additional data should be collected.

- Assessment of continued consent / assent (where applicable).
- Fasting blood and urine sampling for safety labs, including HbA1c.
- Collect blood sample for plasma retention and storage.
- Collect blood samples for PK and PD.
- Provide subject with a meal/snack.
- Check blood sugar, using point of care device, after an appropriate time.
 - If subject is hypoglycemic (<90mg/dL), feed the subject again and re-check blood sugar prior to neuropsychological assessments.
 - If subject is hyperglycemic (>300mg/dL), reschedule the neuropsychological assessments for a proximal day within the visit window.
- MMSE, ADAS-cog14, CDR-sb, FAQ, Amsterdam-IADL, NPI, DEMQOL-proxy.
- C-SSRS.

- Review and record new concomitant medications.
- Assess symptoms/adverse events by asking the participants to respond to a non-leading question such as “How have you been feeling?”
- Brief physical and neurologic examination.
- Body weight.
- 12-lead electrocardiogram (ECG) after 5 minutes rest.
- Vital signs: blood pressure (supine), pulse rate after 5 minutes rest.

6.3.11 Part 2 / Early Termination

In the event a subject discontinues participation prior to completion of the Month 18 Visit and less than 45 days have elapsed since the subject’s last dose of study drug, the Early Termination Visit should be completed performing the study procedures as follows. In all cases, a Follow-up Visit (as described in Section 6.3.10) should be performed approximately 3 months after the last dose of study drug. However, if a participant withdraws consent prior to early termination, no further evaluations should be performed, and no additional data should be collected.

- Assessment of continued consent / assent (where applicable).
- Fasting blood and urine sampling for safety labs, including HbA1c.
- Collect blood sample for plasma retention and storage.
- Collect blood samples for PK and PD.
- Provide subject with a meal/snack.
- Check blood sugar, using point of care device, after an appropriate time.
 - If subject is hypoglycemic (<90mg/dL), feed the subject again and re-check blood sugar prior to neuropsychological assessments.

- If subject is hyperglycemic ($>300\text{mg/dL}$), reschedule the neuropsychological assessments for a proximal day within the visit window.
- MMSE, ADAS-cog14, CDR-sb, FAQ, Amsterdam-IADL, NPI, DEMQOL-proxy.
- C-SSRS.
- Review and record new concomitant medications.
- Assess symptoms/adverse events by asking the participants to respond to a non-leading question such as “How have you been feeling?”
- Brief physical and neurologic examination.
- Body weight.
- 12-lead electrocardiogram (ECG) after 5 minutes rest.
- Vital signs: blood pressure (supine), pulse rate after 5 minutes rest.
- Return study drug.
- Drug accountability. Any discrepancies are recorded in the source.
- Brain MRI. For subjects with a contraindication to MRI scanning (e.g., pacemaker), no brain MRI is required for this visit.

6.4 SUBJECT WITHDRAWAL

Participants may withdraw from the study at any time at their own request or the request of their study partner, caregiver/informant/guardian, or they may be withdrawn at any time at the discretion of the Investigator or Sponsor for safety, behavioral, compliance, or administrative reasons. If a participant does not return for a scheduled visit, every effort should be made to contact the participant including certified letter, return receipt requested. The investigator should inquire about the reason for withdrawal, request that the participant return all unused investigational product(s), request that the participant return for any remaining clinic visits.

If the participant withdraws from the study and joins another clinical study or does not wish to complete the remaining clinic visits, an Early Termination and/or Follow-up Visit should be performed as follows:

- An Early Termination should be performed if less than 45 days have elapsed since the subject's last dose of study drug.
- A Follow-up Visit should be performed when \geq 45 days have elapsed since the subject's last dose of study drug.

Continued follow-up with the participant may be required if there are any unresolved adverse events (refer to Section 8.7).

If the participant withdraws from the study, and also withdraws consent for disclosure of future information, no further evaluations should be performed, and no additional data should be collected. The Sponsor may retain and continue to use any data collected before such withdrawal of consent. An individual patient enrolled in the trial may be discontinued from dosing (and continue in the study) based on a specific adverse event profile as recommended by either the IDMC and/or the Sponsor in discussions with the PI. The IDMC or the Sponsor may temporarily stop dosing of enrolled subjects and/or additional enrollment of new patients at any time and may permanently terminate the study at any time.

Any emergent medical condition or safety finding that, in the opinion of the Investigator, may jeopardize the participant's safety if he/she continues dosing will be sufficient reason to discontinue dosing (temporarily or permanently), while the participant continues in the study. The participant should be followed as indicated for the AE until resolved, declared stable or the participant is lost to follow up. Safety data will be obtained from the physical and neurological examination, vital signs, routine laboratory tests, ECG, and neuropsychological testing batteries. Once resolved, the Investigator and Medical Monitor may discuss if it would be appropriate to re-start dosing.

7.0 ASSESSMENTS

7.1 SAFETY AND TOLERABILITY

7.1.1 Body Measurements

Height (cm) will be measured at the Screening Visit, without shoes.

Body weight (kg) will be measured on the same scale without shoes, coats, or sweaters.

BMI will be calculated as body weight (kg) / height (m)².

7.1.2 Vital Signs

Vital signs measurements will consist of blood pressure and pulse rate while the participant is supine. Vital signs will be conducted at all the study visits. Participant should have been supine at least 5 minutes prior to vital signs determination. At Baseline, pre-dose measurements will be performed in triplicate; all other vital signs readings (at time points shown in the Schedule of Activities) will be a single measurement. The baseline triplicate readings for blood pressure will be averaged for eligibility determination.

7.1.3 Electrocardiogram

12-lead ECG should be recorded after participants have been resting at least 5 minutes in the supine position. Digital ECG tracings will be performed using equipment from and analyzed by a central ECG laboratory. The cardiologist reading the ECGs will be blinded regarding study drug assignment. All standard intervals will be measured.

When assessing eligibility at the Screening visit, the presence of BBB (either left or right) is allowable as long as the absolute QTcF value does not exceed 500 msec and the subject does not have any other cardiac exclusions as described in exclusion criterion 19. When an ECG displays a paced rhythm indicating a functioning pacemaker is present, there is no upper QTcF limit as long as there are no related cardiac exclusions (reference exclusion criterion 20). Note: If there is no known

history of BBB (either right or left), the discovery of such should prompt further investigation prior to proceeding with screening.

At the Baseline visit, the participant will have an ECG obtained (in triplicate) in order to verify continued eligibility for the study. If the QTcF is >470 msec is determined based on the average of the 3 QTcFs obtained from the local reading, a subject should not be dosed, pending central reading of the ECG.

When the site receives the Baseline Visit Central ECG Laboratory reading(s), if QTcF is confirmed as exclusionary (using the criteria immediately above), the subject should be excluded. If the central reading does not confirm the exclusion, the patient may be dosed as soon as convenient/possible. If a patient was dosed based on local reading that determined to be acceptable (using the criteria above) and the central reading is nevertheless determined to be exclusionary, the site should contact the Sponsor for guidance on how to proceed.

At any time during the study, a subject with any of the above ECG values should prompt a call to the Sponsor for guidance on how to proceed.

7.1.4 Physical Examination

Complete physical examination will include skin, eyes, ears, nose and throat, cardiac, respiratory, abdomen, and extremities. Complete physical examination will be conducted at the Screening visit. Brief physical examination will include skin, eyes, oral mucosa, cardiac, and respiratory, and a directed exam related to any reported AEs. A brief physical examination will be conducted at all the study visits. Body weight will be also examined at all study visits.

Clinically relevant findings noted at Screening will be considered medical history. Any treatment emergent new finding on brief physical examination will be documented as an adverse event.

7.1.5 Neurological Examination

Complete neurological examination will include cortical function, meningeal irritation assessment, cranial nerves, motor and sensory function, coordination, deep

tendon reflexes, stance and gait. Complete neurological examination will be conducted at Screening.

Brief neurological examination will include meningeal irritation assessment, cranial nerves, motor and sensory function, coordination, deep tendon reflexes, stance and gait. Brief neurological examination will be conducted at all the study visits.

Clinically relevant findings noted at Screening will be considered medical history. Any treatment emergent new finding on brief neurological examination will be documented as an adverse event.

7.1.6 Laboratory

7.1.6.1 Standard Safety Laboratory Tests

Unless noted otherwise, safety laboratory tests will be performed in the fasted state, according to the Schedule of Activities in [Table 1](#) and [Table 2](#). All routine laboratory tests will be analyzed by a central laboratory that will provide instructions and supplies.

Hematology	Chemistry	Urinalysis	Other ^c
Hemoglobin	BUN and Creatinine	pH	FSH ^b
Hematocrit RBC count	Plasma Glucose (fasting)	Glucose (qual) Protein (qual) Blood (qual)	Urine drug screen
Platelet count WBC count	Calcium	Ketones Nitrites	T3, T4, TSH
MCV	Sodium	Leukocyte esterase	Vitamin B12
Total neutrophils (Abs)	Potassium	Microscopy ^a	Hepatitis B, C
Eosinophils (Abs)	Chloride		
Monocytes (Abs)	Total CO2 (Bicarbonate)		
Basophils (Abs)	AST		
Lymphocytes (Abs)	ALT		
	GGT		
	LDH		
	Total Bilirubin		
	Alkaline phosphatase		
	Uric acid		
	Albumin		
	Total protein		
	HbA1c		
	Insulin		
	eGFR calculation		

^a Only if urine dipstick is positive for blood, protein, nitrites or leukocyte esterase.

^b Females.

^c At screening.

- Hepatitis screens include hepatitis B surface antigen, hepatitis B core antibody, hepatitis B surface antibody, and hepatitis C antibody.
- Minimum requirement for urine drug testing includes: cocaine, THC, opiates, benzodiazepines and amphetamines.

7.1.6.2 Assessment of Blood Glucose Using Point of Care Device

An on-site point of care blood glucose measurement must be obtained prior to neuropsychological assessments. The point of care blood glucose measurement should be obtained after an appropriate time following the low carbohydrate / high protein meal or snack (e.g., 30-60 minutes). The blood glucose measurement obtained using the point of care device will only be documented in the source documents and used to determine if it is appropriate to proceed with neuropsychological assessments.

The blood glucose measurement from the central laboratory will be the measurement included in the study database.

7.1.6.3 Assessment of Potential Cases of Drug Induced Liver Injury

Abnormal values in aspartate transaminase (AST) and/or alanine transaminase (ALT) concurrent with abnormal elevations in total bilirubin that meet the criteria outlined below, in the absence of other causes of liver injury, are considered potential cases of drug-induced liver injury. These events should be considered important medical events and reported as serious adverse events.

Participants who present with the following laboratory abnormalities should be evaluated further to definitively determine the etiology of the abnormal laboratory values:

- a. Participants with AST or ALT baseline values within the normal range who subsequently present with AST or ALT ≥ 3 times the upper limit of normal concurrent with a total bilirubin ≥ 2 times the upper limit of normal with no evidence of 1) hemolysis, 2) cholestasis (elevated alkaline phosphatase ≥ 2 times the upper limit of normal or not available) or 3) Gilbert's Syndrome (common benign condition associated with intermittent elevations of primarily indirect, unconjugated, bilirubin to about 2 X upper limit of normal.)

b. Participants with pre-existing AST or ALT baseline values above the normal range who subsequently present with AST or ALT ≥ 2 times the baseline values and ≥ 3 times the upper limit of normal concurrent with a total bilirubin ≥ 2 times the upper limit of normal with no evidence of 1) hemolysis, 2) cholestasis (elevated alkaline phosphatase ≥ 2 times the upper limit of normal or not available) or 3) Gilbert's Syndrome (common benign condition associated with intermittent elevations of primarily indirect, unconjugated, bilirubin to about 2 X upper limit of normal.)

Increases defined above should be confirmed with repeat testing within 48 to 72 hours. In addition to repeating AST and ALT, laboratory tests should include albumin, amylase, creatine kinase, total bilirubin, direct and indirect bilirubin, gamma-glutamyl transferase (GGT), international normalized ratio (INR) and alkaline phosphatase. Symptoms should be assessed. The medical monitor should be contacted to discuss the patient's condition.

Close observation should be immediately initiated if symptoms persist and/or repeat testing confirm the abnormalities described above. Evaluation should include repeating laboratory tests (two or three time weekly; frequency may decrease to once a week or less if abnormalities stabilize or trial drug is discontinued and the subject is asymptomatic), and a detailed medical history and physical assessment. A detailed history, including relevant information, such as history of symptoms or concurrent illnesses, concomitant medication use (including review of acetaminophen use and herbal/dietary supplements), alcohol consumption, recreational drug use and special diets. Additionally, family history, sexual history, travel history, history of contact with a jaundiced subject, surgery, blood transfusion, history of liver or allergic disease, and work exposure, should be collected. Ruling out acute hepatitis A, B, C, D, and E infection, autoimmune or alcoholic hepatitis, NASH, hypoxic/ischemic hepatopathy, Epstein-Barr virus, cytomegalovirus, herpes simplex virus, toxoplasmosis, varicella, parvovirus and biliary tract disease (gall bladder/ductal imaging may be warranted).

All cases confirmed on repeat testing, with no other cause for LFT abnormalities identified at the time should be considered potential drug induced liver injury irrespective of availability of all the results of the investigations performed to determine etiology of the abnormal LFTs.

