20. Participants demonstrating QTcF > 470 msec on Screening 12-lead ECG (confirmed with a repeat measure). Participants with known history of bundle branch block (either right or left) are allowed if QTcF value does not exceed 500 msec. Participants with a functioning pacemaker, indicated by an ECG displaying paced rhythm, are allowed with no QTcF upper limit.
21. History of diabetic ketoacidosis within the last year.
22. History of more than one severe episode of hypoglycemia that required assistance by a third party within the past year.
23. History of chronic pancreatitis.
24. Current clinically significant hepatic disease or elevated LFTs ≥ 2 times the upper limit of normal (ULN) at Screening.
25. Stage 4 kidney disease (estimated GFR < 30 mL/min/1.73 m², as calculated by the CKD-EPI equation [Levey 2009]).
26. Any laboratory value not already specified above that is outside the laboratory reference range and considered by the Principal Investigator, or appropriately qualified designee, to be a clinically significant abnormality.
27. Use of insulin therapy.
28. Any other medical condition or reason that, in the opinion of the Principal Investigator or appropriately qualified designee, makes the subject unsuitable to participate in this clinical trial.

Eligibility for randomization will be reviewed and approved by an independent Randomization Authorization Committee. The remit of this committee will be to ensure each patient deemed by the Investigator to be eligible for the trial meets key eligibility criteria and is suitable for participation in the study.

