6.9.4 Routine Clinical Laboratory Measurements

Because “exacerbations” of pre-existing abnormalities in laboratory analytes are examined using clinical judgment and are reported as TEAEs, additional analysis on TEAVs is limited to subjects with values that are normal prior to dosing and abnormal after dosing. Potentially

clinically significant abnormalities in laboratory analytes are to be reported as TEAEs and summarized as clinical TEAEs.

Subjects with clinical laboratory data meeting the criteria in Section 10 of this SAP for values of potential clinical concern will be identified and summarized. Proportions of subjects with clinical laboratory values of potential clinical concern will be examined for the treatment groups.

For each post-Baseline assessment, descriptive statistics are provided for the assessment value and the change from Baseline to the assessment with mean, median, standard deviation, minimum, and maximum at each assessment time. Liver Function Tests

Liver function tests have additional analysis views for this study in accordance with current regulatory guidance. To explore the potential for drug-induced liver injury consistent with *Guidance for Industry "Drug-induced liver injury: premarketing clinical evaluation"* (CDER, CBER, July 2009), subjects will be summarized and listed who meet the following criteria:

- (1) Elevations in either AST or ALT of at least 3-times the upper limit of normal, and
- (2) An accompanying abnormal bilirubin.

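### Read literally, Protocol 7.1.6.3 treats a missing alkaline phosphatase as cholestasis and so drops the participant from the liver-injury trigger: a minor wording correction to a safety rule

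*Protocol*

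**What the plan says.** Protocol 7.1.6.3 has two triggers. Limb (a) covers participants with normal AST or ALT at baseline: AST or ALT at least 3 × ULN with total bilirubin at least 2 × ULN. Limb (b) covers a raised baseline and also requires AST or ALT to be at least twice the baseline value. Each limb then requires no evidence of three other explanations: hemolysis, cholestasis and Gilbert's Syndrome. The second is described in the same words in both limbs: "cholestasis (elevated alkaline phosphatase ≥ 2 times the upper limit of normal or not available".

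Three instructions depend on these limbs:

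- The SAE rule: "These events should be considered important medical events and reported as serious adverse events".
- Further evaluation to establish the cause.
- Repeat testing: "Increases defined above should be confirmed with repeat testing within 48 to 72 hours". The repeat panel includes "gamma-glutamyl transferase (GGT), international normalized ratio (INR) and alkaline phosphatase".

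The closing paragraph says that cases confirmed on repeat testing, with no other cause found at the time, "should be considered potential drug induced liver injury irrespective of availability of all the results of the investigations performed".

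Protocol 7.1.6.1 places ALP in the central chemistry panel alongside AST, ALT and total bilirubin. SAP 6.9.4 has its own liver display: "subjects will be summarized and listed who meet the following criteria", namely AST or ALT at least 3 × ULN and "An accompanying abnormal bilirubin". It sets no ALP condition.

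**The concern.** Cholestasis is a reason to leave a case out of the trigger, so the words about an unavailable result fall on the excluding side. A test that was not done then counts as evidence of another cause. For a combined aminotransferase and bilirubin rise, a missing ALP should lead to more testing, not less.

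The wording is also circular. The panel that would supply the missing ALP is ordered only for increases that already meet the definition, and the definition fails because the ALP is missing.

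What is at stake is the timing of work-up and reporting. If the repeat is not triggered, the next scheduled chemistry panel is about 90 days later (Days 90, 180 and 270 in Part 1; every three months in Part 2) rather than 2 to 3 days later. Between clinic visits in Part 1 there are only telephone contacts.

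**Working it through.** No calculated figure in the plan is involved. The check is to write the rule as logic and run each ALP state through it.

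**Inputs** (Protocol 7.1.6.3): AST/ALT limit 3 × ULN; bilirubin limit 2 × ULN; exclusions H (hemolysis), C (cholestasis), G (Gilbert's); for limb (b), the extra condition AST or ALT ≥ 2 × baseline.

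**Rule.** Flagged = (AST or ALT ≥ 3 × ULN) AND (bilirubin ≥ 2 × ULN) AND NOT H AND NOT C AND NOT G. Limb (b) adds AND (AST or ALT ≥ 2 × baseline).

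- As written: C = (ALP ≥ 2 × ULN) OR (ALP missing).
- Corrected: C = (ALP measured AND ≥ 2 × ULN).

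**Result** for a participant who meets the enzyme and bilirubin limits, without hemolysis or Gilbert's:

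| ALP state | As written | Corrected |
|---|---|---|
| < 2 × ULN | flagged | flagged |
| ≥ 2 × ULN | not flagged | not flagged |
| missing | **not flagged** | **flagged** |

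One of three states changes. The result is the same for limb (b) once its baseline multiple is met. Both limbs carry the same parenthesis, so neither corrects the other.

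**What follows from not being flagged.** The SAE instruction refers to events meeting the criteria, the evaluation refers to participants with the listed abnormalities, and the repeat test refers to the increases defined above it. All three point back to the same limbs.

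**Whether the closing paragraph repairs this.** It tells the site not to wait for every investigation result, which is the right intent. But it applies to cases already confirmed on repeat testing. A participant who never enters the trigger has no mandated repeat and so does not reach that sentence.

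**How often the rule is applied.** Tables 4 and 5 of Protocol 7.10 give 2 on-treatment routine panels plus 1 at follow-up in Part 1, and 6 plus 1 in Part 2. With full attendance:

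- Part 1, 43 enrolled (SAP 1.4): 43 × 2 = 86 on-treatment panels, and 43 × 3 = 129 with follow-up.
- Part 2, 200 planned (Protocol 3.0): 200 × 6 = 1,200, and 200 × 7 = 1,400 with follow-up.

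These are upper counts of scheduled panels, not of cases. A case needs both laboratory limits to be met, no hemolysis or Gilbert's, and ALP alone missing from the panel. The documents give no rate for any of these, so no expected number is claimed.

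**The case against.** The best answer is that the harmful reading is not the only one. The exclusion calls for evidence of cholestasis, and an absent test is not evidence. The increases to be repeated could mean just the enzyme and bilirubin rises. With the closing paragraph, the parenthesis then looks like a garbled phrase in a section whose purpose is plain. This stands as an account of intent: nothing suggests the sponsor chose to exclude participants with a missing ALP. It does not settle the rule. The parenthesis says expressly that an unavailable result falls under cholestasis, and no other sentence clearly overrides it. The softer reading of the repeat-test sentence would also leave the SAE rule unrepaired.

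The second answer is reach, and it largely stands. ALP is drawn with AST, ALT and bilirubin, so it would have to be missing alone. Other routes stay open:

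- An abnormal result that needs further diagnostic testing is an AE (Protocol 8.1).
- It can be an SAE as an important medical event (8.5).
- Clinically significant laboratory abnormalities are followed up (8.7).
- Appendix 1 flags AST or ALT above 3 × ULN and bilirubin above 1.5 × ULN whatever the ALP; SAP section 11 repeats these limits.
- Ongoing safety review (9.8) and the IDMC (9.13) continue.

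Most of these depend on judgment or on later review. Section 7.1.6.3 exists to make this pattern automatic.

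A reader might infer that such a participant would also vanish from the end-of-study liver display. The documents do not support that, because the SAP 6.9.4 criteria do not mention ALP. A reader might also see faults in the SAP itself: that 6.9.4 is looser on bilirubin than the protocol, or that 8.6 keeps unscheduled values out of summaries. Neither holds as a defect. The 6.9.4 criteria are a wider screen that loses no protocol case on the same values, and the subjects are also listed. The later sentences of 8.6 admit unscheduled data to summaries over time and keep them out of by-visit summaries, so the section can be read consistently.

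**Conclusion.** The wording is wrong as it stands. On a literal reading, a missing ALP removes a participant with the defining enzyme and bilirubin pattern from the evaluation, the repeat panel and the automatic SAE rule, contrary to the intent of the section's own closing paragraph. The error affects real-time work-up and reporting, not the final liver display.

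It is minor in size: one of three ALP states, needing an isolated missing result on a shared panel, with general safety routes still in place. This rests on two assumptions. One is that sites apply the parenthesis as written. The other is that ALP is seldom missing alone, which the shared panel makes likely but for which the documents give no figure. It is still worth correcting because it is an operative safety rule and the same section governs Part 2.

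**What to change.** In Protocol 7.1.6.3, limbs (a) and (b), change item 2 to: *cholestasis (measured ALP ≥ 2 × ULN)*. After the two limbs add: *A missing ALP does not exclude a case; obtain it with the repeat panel.* The medical lead should confirm the wording.

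Do not simply put the non-cholestatic range (ALP below 2 × ULN, or not available) into the existing parenthesis. The list is governed by a negative, so that would literally exclude participants with ALP below 2 × ULN, the core pattern, and still exclude those with a missing ALP. Inserting a full clause saying there is no cholestasis would create a double negative.

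The cost is one phrase in two places and one added sentence. No test is added, since ALP is already in both the routine and the repeat panels. Classification of participants with a measured ALP does not change, and the SAP needs no edit.
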